**Table 4 Adverse event relatedness categories**

| Term       | Definition   |
|------------|--|
| Unrelated  | No evidence that AE related to Aquablation procedure or AQUABEAM System  |
| Unlikely   | AE has a low likelihood of being related to Aquablation procedure or AQUABEAM System                               |
| Possible   | AE could be related to Aquablation procedure or AQUABEAM System but an alternative explanation is also likely      |
| Probably   | AE likely to be related Aquablation procedure or AQUABEAM System even though alternative explanations are possible |
| Definitely | AE almost certainly related to Aquablation procedure or AQUABEAM System  |

**Table 5 Clavien-Dindo grading system^7**

| Grade    | Definition  |
|----------|---|
| Grade 1  | Any deviation from the normal postoperative course without the need for pharmacological treatment or surgical, endoscopic and radiological interventions
Allowed therapeutic regimens are: drugs as antiemetics, antipyretics, analgetics, diuretics and electrolytes and physiotherapy. This grade also includes wound infections opened at the bedside.† |
| Grade 2  | Requiring pharmacological treatment with drugs other than such allowed for grade I complications. Blood transfusions and total parenteral nutrition are also included.*   |
| Grade 3  | Requiring surgical, endoscopic or radiological intervention.  |
| Grade 3a | Intervention not under general anesthesia.  |
| Grade 3b | Intervention under general anesthesia.  |
| Grade 4  | Life-threatening complication (including CNS complications: brain haemorrhage, ischaemic stroke, subarachnoid bleeding, but excluding transient ischaemic attacks) requiring IC/ICU management.   |
| Grade 4a | Single organ dysfunction (including dialysis).  |
| Grade 4b | Multi-organ dysfunction.  |
| Grade 5  | Death of a subject.   |

\*Note that the need for medications related to BPH (e.g., alpha blockers) is likely related to lack of effectiveness (not safety) and is not considered to meet criteria for a Grade 2 event.

†This includes the following: persistent ejaculatory dysfunction, erectile dysfunction or urinary incontinence and urinary retention requiring re- catheterization after 3 days post-procedure. Note that bladder catheterization itself is considered a Clavien-Dindo Grade 1 event

## 2.21 Study Withdrawal

Subjects may be terminated or withdrawn from the study for the following reasons:

- Voluntary withdrawal: the subject voluntarily chooses not to further participate in the study.
- Subject death.

- At the discretion of the Principal Investigator, or where the ongoing participation of the patient involves a risk greater than perceived benefit.
- The Sponsor may terminate the study at any time.

### ***2.22 Lost to Follow-Up***

A subject will be considered “lost to follow up” and terminated from the study when he can no longer be reached by study staff and has missed two consecutive follow up visits. Documentation of the unsuccessful attempts by the Investigator or his/her designee to contact the subject or next of kin need to be filed with the study exit form.

### ***2.23 Study Termination***

The sponsor has the right to discontinue the study at any time for any reason.

### ***2.24 Case Report Forms (CRF)***

Data will be entered into an EDC system. If a consented subject is not treated, a study exit form will be completed to record the reason for screen fail or withdrawal.

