### ***4.2 Primary Endpoint Calculation and Sample Size Determination***

Prior studies have shown that IPSS scores are reduced by approximately 16 points after Aquablation, values similar to those observed after TURP. In patients with moderate-to-severe BPH, the mean change in IPSS score representing slight improvement is approximately 5 points. Therefore, showing a mean reduction in IPSS scores that statistically exceeds  $16-5 = 11$  points will be interpreted as study success. The study's primary endpoint hypothesis is a one-way statistical test (alpha=.025 for interpretation):

$$\begin{aligned} H_0: \text{Mean(IPSS change score at 3 months)} &\leq 11 \\ H_a: \text{Mean(IPSS change score at 3 months)} &> 11 \end{aligned}$$

With 100 patients and assuming 10% subjects lost to follow, 90 evaluable subjects with an underlying change of 16 points and a change score SD of 7.5 points yields a 99% power to detect an improvement of more than 11 points.

The WATER study (IDE#G150089) used an assumption that a TURP rate for the same safety definition provided in this protocol would be 65% for a range of prostate sizes 30-80mL. The same safety target will be used for this protocol treating large prostates of 80-150mL. The assumed true rate for the Aquablation patients will be 50% (10% greater than WATER in order to account for treating larger prostates). The study's primary endpoint hypothesis is a one-way statistical test (alpha=.025 for interpretation):

$$\begin{aligned} H_0: \text{Mean (safety rate at 3 months)} &\geq 65\% \\ H_a: \text{Mean (safety rate at 3 months)} &< 65\% \end{aligned}$$

The primary safety endpoint with 90 evaluable subjects has an 80% power to detect a safety rate of less than 65%.

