#### **4.1 Modified Intent-to-Treat (mITT) Cohort**

The mITT population includes all enrolled subjects in whom the Aquablation handpiece is inserted into the penile urethra. A patient found at the time of the procedure to have a condition that results in study exclusion does not contribute to the mITT cohort. The mITT population is the primary analysis population for both the primary safety and effectiveness endpoints.

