#### **4.3 Safety Cohort**

The safety analysis population includes all subjects in whom Aquablation is initiated. This cohort is used for most safety analyses.

---

\* See <https://cran.r-project.org/>

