## **5 STUDY ENDPOINTS**

### **5.1 Primary Effectiveness Endpoint**

The primary effectiveness endpoint is the IPSS change score from baseline to 3 months. IPSS is an accepted and commonly used measure for symptom severity in BPH. IPSS varies from 0 (no symptoms) to 35 (maximal symptoms). The mean 3-month IPSS change score (abbreviated dIPSS3) in WATER was 16 points (SD=7 points). WATER used a non-inferiority margin of 5 points; 5 points represents the minimum change for men with moderate-to-severe BPH that is detectable. The current study's goal is therefore to show that the IPSS change score statistically exceeds 16-5 = 11 points. The study's hypotheses are therefore:

$$\begin{aligned} H_0: \text{dIPSS}_3 &\leq 11 \\ H_a: \text{dIPSS}_3 &> 11 \end{aligned}$$

A one-way t test with the mITT cohort will be used for the calculation. With 100 patients and assuming 10% subjects lost to follow, 90 evaluable subjects with an underlying change of 16 points and a change score SD of 7.5 points yields a 99% power to detect an improvement of more than 11 points.

A secondary goal is to show similarity of change scores between WATER II and WATER. Data from WATER and WATER II will be combined. Regression analyses controlling for baseline IPSS score (a strong predictor of change scores) will calculate differences in change scores between WATER and WATER II subjects. WATER II will be determined to have similar dIPSS3 scores if the 95% confidence limits for the difference between WATER and WATER II Aquablation subjects exceeds -5 points. The study is not necessarily powered for this comparison.

Missing data for dIPSS3 will be imputed using the following rules:

- Predicted value from baseline IPSS: In WATER, dIPSS3 was strongly and statistically significantly related to baseline IPSS (Figure 1). This finding is not surprising for maximally effective procedures that reduce scores to close to maximal (i.e., a ceiling effect). A linear regression model using WATER II available data will be used to predict missing change scores.
- Low value: A change score of 0 points
- High value: a change of 5 less than the maximal possible improvement, which represents change scores from WATER (see also Figure 1)

[figure not shown]

Figure 1. Relationship between baseline IPSS and 3-month change score in WATER. Blue = Aquablation, red = TURP.

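### SAP 5.1 names no primary imputation rule, and its regression rule can give a man who leaves before month 3 a retained man's improvement while ignoring his 1-month IPSS

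*Protocol*

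**What the plan says.** **Who is analysed.** SAP 4.1 makes mITT the primary population for both primary endpoints and defines it by insertion: "The mITT population includes all enrolled subjects in whom the Aquablation handpiece is inserted into the penile urethra". It removes men found at the procedure to have an excluding condition. SAP 4.3 uses a later event: "The safety analysis population includes all subjects in whom Aquablation is initiated". A man with insertion but no Aquablation can therefore be in mITT.

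**How men leave.** Protocol 2.21 lists among the grounds for withdrawal: "At the discretion of the Principal Investigator, or where the ongoing participation of the patient involves a risk greater than perceived benefit". Under 2.25, participation is complete at 60 months, on withdrawal or on loss to follow-up, and an exit form is filled in. Protocol 2.24 covers the untreated: "If a consented subject is not treated, a study exit form will be completed to record the reason for screen fail or withdrawal". Table 2 has no exit visit, but it does schedule IPSS at month 1.

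**How a missing change is scored.** SAP 5.1 lists three rules: a value predicted from baseline IPSS ("A linear regression model using WATER II available data will be used to predict missing change scores"), a low value of 0, and a high value 5 points short of the maximal possible improvement. It does not say which is primary, which are sensitivity analyses, or whether the reason for missingness matters.

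**The concern.** The procedure is done once. Withdrawing a man afterwards does not stop his treatment; it stops only the collection of his data. The data available for the regression come from men with an observed 3-month score. A man who leaves before month 3 because he did badly is therefore scored like a retained man with the same baseline. If he attended month 1, post-treatment evidence about him exists and the rule does not use it. An mITT man with insertion but no Aquablation, if there is one, would be scored the same way.

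The estimated mean improvement is at stake. If the missing men did worse than the retained men, it is inflated. With no rule named primary, the choice could also be made after the data are seen.

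**Working it through.** **Inputs from the documents.** Success means a mean change above 11 (SAP 5.1). The test is a "one-way statistical test (alpha=.025 for interpretation") one. Planning: "With 100 patients and assuming 10% subjects lost to follow", and "90 evaluable subjects with an underlying change of 16 points and a change score SD of 7.5 points yields a 99% power". Protocol 2.11 gives 101 treated men.

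**1. The plan's own figure.** Power = Φ(5/7.5 × √90 − 1.96) = Φ(6.32 − 1.96) = Φ(4.36) = 0.99999. The noncentral t with 89 df gives the same. The stated 99% reproduces, read as at least 99%.

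**2. Shift in the mean from k such men.** Shift = k × (16 − true change)/101, taking 16 as the predicted value.

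| k | true change 0 | true change 5 |
|---|---|---|
| 1 | 16/101 = 0.16 | 11/101 = 0.11 |
| 3 | 48/101 = 0.48 | 33/101 = 0.33 |
| 10 | 160/101 = 1.58 | 110/101 = 1.09 |

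Ten is the plan's whole 10% loss, all assumed to be of this kind.

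**3. Does success survive at planning values?** Take N = 101, with 91 men observed (mean 16, SD 7.5) and ten scored 0.
- Mean = 16 × 91/101 = 14.42.
- Sum of squares = 90 × 7.5² + 91 × (16 − 14.42)² + 10 × 14.42², so SD = 8.58.
- Lower 97.5% bound = 14.42 − 1.984 × 8.58/√101 = 12.72.

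With N = 100 the mean is 14.40 and the bound 12.69. Under regression the mean stays at about 16.0 and the bound is about 14.6. About 20 men scored 0 are needed before the bound reaches 11 (10.96 with N = 100, 11.00 with N = 101).

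**4. Where the choice of rule matters.** Simulated probability of success, N = 100, ten missing. Assumptions not in the documents: baseline IPSS 23 (SD 6), correlation of baseline with change 0.6.

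| True mean of observed men | regression rule | 0-point rule |
|---|---|---|
| 16 | about 100% | 99.3% |
| 14 | 98% | 49% |
| 13 | 77% | 10% |

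Hand check at 13:
- Regression: the mean must exceed 11 + 1.984 × 7.23/√100 = 12.43. The sampling SD is 7.5/√90 = 0.79, so Φ((13 − 12.43)/0.79) is about 0.76.
- 0-point: the mean is 0.9 × 13 = 11.7 and must exceed 11 + 1.984 × 8.11/√100 = 12.61. The sampling SD is 0.9 × 0.79 = 0.71, so Φ(−1.28) is about 0.10.

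**5. False success at the boundary.** Suppose the true mean over all mITT men is exactly 11 and the missing men truly change by 0. The regression rule then declares success about 3.7% (one man), 7% (three), 13% (five) and 40% (ten) of the time, against a nominal 2.5%. For ten men the range is 39% to 41% as the assumed correlation runs from 0.8 to 0. If the missing men truly change by 5 (N = 101), the figures are about 3%, 5%, 7% and 17%. When the true change is 0, scoring these men 0 keeps the rate at or below 2.5%.

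**The case against.** - **The SAP does not rely on regression alone.** A reader might infer that leavers are scored from baseline IPSS only. The documents do not support that: the 0-point rule stands beside the regression and is a harsh bound. What remains is that no rule is named primary or made a required sensitivity analysis.
- **Protocol 2.24 does not end follow-up.** It is a case-report-form rule, and 2.25 does not list being untreated as an exit reason. That untreated men stop being followed is an inference. The point rests on 2.21 with 2.25.
- **The inserted-but-untreated group may be empty.** SAP 4.1 removes men found ineligible at the procedure, and protocol 2.11 describes the 101 as treated. The 84 earlier procedures in protocol 2.2, all technically successful, might look like a way to bound the rate. They cannot, because those men had all undergone Aquablation. The documents give no rate.
- **Nothing says that men with poor results are the ones withdrawn.** True. Selective exit is a possibility that the rules leave open, not a documented event. Protocol 2.22 also requires two consecutive missed visits before a man is lost to follow-up, so one missed visit does not remove him.
- **The trial passes anyway at planning values.** True, and this limits the weight of the point.

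**Conclusion.** The concern holds in a limited form. The regression rule uses baseline IPSS from men with observed outcomes, ignores the 1-month score, and is not ranked against the two rules listed with it. Investigator withdrawal can end follow-up with nothing more than a form. If the men missing at month 3 did worse than the retained men, the mean change is inflated: by 0.11 to 0.16 points per man, and by 1.1 to 1.6 in the extreme case of ten.

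These figures assume a predicted change of 16, n = 101 and a true change of 5 or 0 in the missing men. The documents report neither how many men left nor why.

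A reader might infer that the success decision is in doubt. At planning values it is not, since ten men scored 0 leave a lower bound of about 12.7. It becomes exposed only if the observed mean falls well below plan, for example to 13 or 14 with ten men missing. Adverse events after such an exit may also go uncollected, but the documents allow no estimate of that effect.

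**What to change.** **(a) SAP 5.1.**
- Predict the missing 3-month change from baseline plus the 1-month IPSS, or the exit IPSS where there is one.
- Fit the model on men in whom Aquablation was initiated.
- Name this rule as primary and make the 0-point rule a required sensitivity analysis.
- Score inserted-but-untreated mITT men without data as 0, a value the SAP already uses.

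**(b) Protocol 2.21 and 2.25.**
- Where consent allows, continue IPSS and adverse-event contact through month 3 after an investigator withdrawal.
- Record IPSS and adverse events at any exit before month 3.

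For men already past month 3, only (a) can help. Since 2.11 describes the 101 as already treated, that may be most or all of them.

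The cost is some wording, a few phone contacts with existing questionnaires, and a mean change that may come out slightly less favourable.

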### ***2.25 Study Exit***

The subject’s participation in the study is considered complete at the end of the 60 months visit or if the subject withdraws from the study or loss to follow-up. A study exit form shall be completed.

## **3 STUDY ENDPOINTS**

### ***3.1 Primary Efficacy Endpoint***

The primary efficacy endpoint is the change in total IPSS score at 3 months as compared to baseline.

### ***3.2 Primary Safety Endpoint***

The primary safety endpoint is the proportion of subjects with adverse events rated as probably or definitely related to the study procedure classified as Clavien-Dindo Grade 2 or higher or any Grade 1 event resulting in persistent disability (e.g. ejaculatory disorder or erectile dysfunction) evidenced through 3 months post treatment. Note that the Clavien-Dindo classification scheme is for grading postoperative complications not events that reflect lack of effective treatment.

### ***3.3 Secondary Endpoints for Marketing Claims***

Secondary endpoints are:

- Length of procedure time as defined as AQUABEAM Handpiece insertion to insertion of indwelling catheter. Mean and 95% confidence intervals will be calculated. There is no statistical hypothesis for this endpoint; it is considered informational.
- Proportion of subjects, who were sexually active at baseline and experienced either ejaculatory or erectile dysfunction (per protocol definitions) at 3 months. An exact binomial confidence interval will be calculated; there is no statistical hypothesis.
- Change from baseline to 3 months in Qmax. For a patient with a urinary catheter in place at the time testing, the Qmax value will be zero. Mean and confidence intervals will be calculated and a historical semi-quantitative comparison will be made with WATER Study data or other studies.

- Change from baseline to 3 months in PVR. For a patient with a urinary catheter in place at the time testing, the PVR value will be Not Applicable. Mean and confidence intervals will be calculated and a similar semi-quantitative comparison will be made.
- Change from baseline to 6 months in PSA. Mean and confidence intervals will be calculated. A t test will be used to compare PSA change vs. a null hypothesis of no change.
- Mean change from baseline in MSHQ-EjD score at 3 months. Preservation of ejaculatory function, meaning a change non-inferior to -4 points. A t test with 95% confidence intervals will be used to evaluate this hypothesis.
- Mean change from baseline in IIEF-5 (aka SHIM, part of IIEF-15) at 3 months. Preservation of erectile function, meaning a change score non-inferior to -6 points. An approach similar to that listed for MSHQ-EjD will be used.
- Re-intervention rate at 3 months. Re-intervention is defined as the need for additional tissue resection following the index procedure. An exact binomial confidence interval will be calculated. No statistical hypothesis is proposed.
- Subjects who entered the trial using a urinary catheter at any time 45 days prior to enrollment will yield more than 50% not needing a catheter at any time 45 days prior to the 3 months visit. An exact binomial confidence interval will be calculated. No statistical hypothesis is proposed.

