## 2.7 Overall Design

Pivotal study to support marketing claims, single-arm, interventional clinical trial collecting data from the use with the AQUABEAM System.

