## **6.3 Change in Qmax**

Change from baseline to 3 months in Qmax, a uroflow measurement. Calculations will be performed with and without patients with a catheter at the time of assessment. The “with” analysis will assume a Qmax of 0 for any patient with a urinary catheter in place at the time testing. Mean and confidence intervals will be calculated using a t test (two-tailed, alpha=.05) against a null hypothesis of no change and a historical semi-quantitative comparison will be made with WATER study data or other studies.

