## **6.6 Change in MSHQ-EjD**

Mean change from baseline in MSHQ-EjD score at 3 months. Preservation of ejaculatory function is defined as a change non-inferior to -4 points. (Note that there is no published minimally clinically important difference for MSHQ-EjD.) A t test with 95% confidence intervals will be used to evaluate this hypothesis. If non-inferiority is concluded, a secondary test will calculate whether the change score represents statistical superiority.

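### Five secondary endpoints listed for marketing claims are tested at unadjusted levels, with no order across endpoints and no requirement that the primary endpoints succeed

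*Protocol*

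**What the plan says.** Protocol 2.7 describes a "Pivotal study to support marketing claims", and Protocol 3.3 carries the heading "Secondary Endpoints for Marketing Claims". Nine endpoints follow.

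- **PSA at 6 months.** Protocol 3.3: "A t test will be used to compare PSA change vs. a null hypothesis of no change". SAP 6.5 makes this two-sided at 5%.
- **MSHQ-EjD and IIEF-5 at 3 months.** Protocol 3.3 and SAP 6.6 and 6.7 test non-inferiority with margins of -4 and -6 points, using 95% confidence intervals.
- **Qmax and PVR at 3 months.** Protocol 3.3 gives only means, intervals and a semi-quantitative comparison with other studies. SAP 6.3 and 6.4 add two-sided 5% t tests "against a null hypothesis of no change". Qmax is analysed both with and without catheterised patients, and neither version is named as decisive.
- **The other four** (procedure time, ejaculatory or erectile dysfunction rate, re-intervention, catheter discontinuation) are stated to have no hypothesis.

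SAP 6.6 contains the only ordering. Once MSHQ-EjD non-inferiority is concluded, "a secondary test will calculate whether the change score represents statistical superiority". SAP 6.7 takes a similar approach to IIEF-5.

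The one-sided level, "alpha=.025 for interpretation", is given for the primary hypotheses only (Protocol 4.2, SAP 5.2). Neither document states an adjustment or an order across the secondary endpoints, or a rule that the primary endpoints must succeed first.

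**The concern.** The plan separates endpoints with a hypothesis from those without one, so the five tested endpoints cannot be read as merely descriptive. The non-inferiority endpoints have margins and a decision rule, and the list is labelled as supporting claims. With five separate chances to reach a favourable conclusion and no joint control, the chance of at least one false one exceeds the level of any single test.

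The link to the primary endpoints also matters. The primary safety endpoint counts persistent ejaculatory and erectile dysfunction as events. The plan does not say what happens to a conclusion that mean sexual function was preserved if the primary safety test fails.

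**Working it through.** **1. The plan's own figures.** The documents give no family-wise error rate for the secondary endpoints. The figures that can be checked are the primary powers in Protocol 4.2.

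- *Efficacy.* "With 100 patients and assuming 10% subjects lost to follow"; then "90 evaluable subjects with an underlying change of 16 points and a change score SD of 7.5 points yields a 99% power". The standardised distance from the 11-point threshold is (16 - 11) / (7.5/√90) = 5/0.791 = 6.32. Power is Φ(6.32 - 1.96) = Φ(4.36), above 99.9%. The stated 99% is met.
- *Safety.* True rate 50%, target 65%, n = 90. A normal approximation gives 0.15/√(0.25/90) = 2.846, and Φ(2.846 - 1.96) = 81.2%. The exact binomial test named in SAP 5.2 rejects at 49 or fewer events (actual level 0.0248) and has power 82.9%. The stated 80% is reproduced and slightly conservative. Under the sponsor's assumptions the safety test therefore fails about 17% (exact) to 20% (stated) of the time.

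**2. Size of the family.** Protocol 3.3 alone gives three tests. The SAP adds Qmax and PVR, making five tested endpoints. The superiority tests for MSHQ-EjD and IIEF-5 follow that endpoint's non-inferiority test. Each such pair stays at one-sided 0.025:

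- With a true change at the margin, only non-inferiority can be falsely concluded.
- With a true change of zero, only superiority can be.

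A simulation for MSHQ-EjD (n = 90, assumed SD 5) gave 2.5% in each case. The two superiority steps therefore add nothing to the count.

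**3. Chance of at least one false favourable result.** Each test has probability 0.025 in the favourable direction. If k tests are independent and all their nulls are true, the chance is 1 - 0.975^k. The upper bound under any dependence is 0.025k.

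| Family | Independent | Upper bound |
|---|---|---|
| Two sexual-function endpoints | 1 - 0.975² = 4.9% | 5.0% |
| Three tests in Protocol 3.3 alone | 1 - 0.975³ = 7.3% | 7.5% |
| Five tested endpoints | 1 - 0.975⁵ = 11.9% | 12.5% |

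**4. Correlation.** The documents give no correlations, so values were assumed. With equally correlated normal test statistics (400,000 simulated draws), the five-endpoint figure is 10.6% at 0.3, 9.1% at 0.5 and 6.3% at 0.8.

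**5. Which nulls are plausible.** The 11.9% requires no true change in Qmax, PVR or PSA after prostate resection. If all three truly improve, a favourable result on them is not an error. The two sexual-function endpoints remain, at 4.9% if independent and at most 5%.

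**The case against.** The strongest reply is that the realistic exposure is small. Nobody expects Qmax, PVR and PSA to stay unchanged after tissue is resected, which leaves about 5% on two endpoints, and less if the two scores are positively correlated. That stands, and it limits the size of the point.

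It can also be said that 2.5% is borrowed from the primary tests and that the documents set no error rate for the secondary family. That is correct. The plan does not break a rule of its own; it lacks one, for endpoints that it lists as supporting claims.

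A reader might infer three stronger things that the documents do not support.

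- *Eight free-standing tests, giving 1 - 0.975⁸ = 18.3%.* That count needs the two superiority tests, which are conditional and add no error, and the WATER similarity comparison. The latter is in SAP 5.1 under the primary endpoint, outside the marketing list, and is described as not necessarily powered.
- *No ordering at all.* SAP 6.6 orders superiority after non-inferiority, and SAP 6.7 follows by analogy. What is missing is order across endpoints.
- *The plan authorises a sexual-function claim after a failed safety test.* No section says which result supports which claim. The plan is silent, and silence is not permission.

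**Conclusion.** The point holds for five tested endpoints. The error rate across them is uncontrolled: 11.9% if all five nulls are true and the tests are independent, about 9% and 6% at assumed correlations of 0.5 and 0.8, and at most about 5% if Qmax, PVR and PSA truly improve. Against the 2.5% level of each primary test, the realistic figure is roughly double. These figures count errors in the favourable direction only.

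This does not affect the primary analyses. It affects what the secondary results can be said to show, chiefly the two claims of preserved sexual function, and it is cheap to settle.

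**What to change.** Add a paragraph to SAP 6 stating the following.

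1. Secondary hypotheses support claims only if both primary hypotheses are met.
2. The five endpoints are then controlled at an overall one-sided 0.025. One option is Holm's procedure, which needs no order and starts at 0.025/5 = 0.005. The other is a fixed sequence in which every test has its place, set before the data are seen, with the 3-month endpoints ahead of 6-month PSA. If Holm is applied before PSA is available, PSA counts as not yet rejected.
3. The deciding Qmax analysis is named: the one that sets catheterised patients to zero, as in Protocol 3.3.
4. Superiority for MSHQ-EjD and IIEF-5 is tested only after that endpoint's non-inferiority is shown, at that endpoint's allotted level. Under Holm, this share must not also be passed to other endpoints while the superiority step is still open.
5. WATER similarity and all endpoints without a hypothesis are descriptive.

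Protocol 2.11 refers to 101 participants already treated. If 3-month results have been seen, an order can no longer be fixed in advance. In that case use Holm, or label the p-values nominal and report the number of tests.

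**Cost.** No patients and no new data. Under Holm, if Qmax, PVR and PSA are all rejected, the first sexual-function test faces 0.025/2 = 0.0125 instead of 0.025. The larger cost comes from item 1: about a 17 to 20% chance, under the sponsor's own assumptions, that the safety test fails and all secondary results become descriptive. The sponsor should accept that knowingly.
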